1.2 Schema

The study design is depicted in Figure 1.

Figure 1 Study Design

- M=MADRS, Wk=Week, V=Visit. At Visits 4, 5, 6, and 7, MADRS will be administered before the morning dose of study intervention.
- A phone call within the first 3 days after Visits 4, 5, 6, and 7.
- The primary diagnosis of major depressive disorder will be confirmed centrally during the pretreatment period.
- Visit 10 will occur at least 14 days after the last dose of study intervention.

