7 DISCONTINUATION OF STUDY INTERVENTION AND PARTICIPANT WITHDRAWAL

7.1 Discontinuation of Study Intervention

Discontinuation of study intervention does not represent withdrawal from the study.

As certain data on clinical events beyond study intervention discontinuation may be important to the study, they must be collected through the participant's last scheduled follow-up, even if the participant has discontinued study intervention. Therefore, all participants who discontinue study intervention prior to completion of the protocol-specified treatment period will still continue to participate in the study as specified in Section 1.3 and Section 8.11.6.

Participants may discontinue study intervention at any time for any reason or be discontinued from the study intervention at the discretion of the investigator should any untoward effect occur. In addition, a participant may be discontinued from study intervention by the investigator or the Sponsor if study intervention is inappropriate, the study plan is violated, or for administrative and/or other safety reasons. Specific details regarding procedures to be performed at study intervention discontinuation are provided in Section 1.3 and Section 8.11.5.

A participant must be discontinued from study intervention but continue to be monitored in the study for any of the following reasons:

- The participant or participant's legally acceptable representative requests to discontinue study intervention.
- The participant's treatment assignment has been unblinded by the investigator, MSD subsidiary, or through the emergency unblinding call center.

- The participant has a medical condition or personal circumstance which, in the opinion of the investigator and/or Sponsor, place the participant at unnecessary risk from continued administration of study intervention.
- The participant has a positive urine or serum pregnancy test. See Section 8.3.6.2 for pregnancy testing requirements.
- The participant has an ALT $\ge 3x$ ULN
- The participant has an AST $\geq 3x$ ULN with total bilirubin $\geq 2x$ ULN and ALP $\leq 2x$ ULN
- The participant has an AST $\ge 3x$ ULN with ALT value ≥ 100 IU/L

Note 1: Liver function tests are to be confirmed by repeat testing within 48 hours of initial test results. If test results are unable to be confirmed within this timeframe, the study intervention should be withheld until test results are available. Study intervention should be discontinued if unable to repeat testing.

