9.3.1 Estimands

In the language of ICH E9(R1) [Food and Drug Administration 2021], there are 4 'intercurrent events' of interest: IE1) discontinuation of study intervention, IE2) discontinuation of stable antidepressant therapy, IE3) initiation of a non-study antidepressant therapy, and IE4) premature unblinding of either the investigator or participant.

Primary Objective

Primary Estimand [based on 'hypothetical strategy' in ICH E9(R1)]

To address the primary objective, an estimand based on HS will be used. This 'HS estimand' is intended to contrast the effect of MK-1942 (daily and intermittent dosing), relative to placebo, when initiated with stable antidepressant therapy under a *hypothetical* scenario in which there is no discontinuation of study intervention nor stable antidepressant therapy, no initiation of a non-study antidepressant therapy, and no premature unblinding of either the investigator or participant during an envisioned follow-up period of up to 4 weeks (with primary assessment at Week 3 for the MK-1942 daily dose group and at Week 1 for the MK-1942 intermittent dose group).

The HS estimand consists of the following attributes:

- Target population: individuals aged 18 to 65 with TRD
- Endpoint: Week 3 change from baseline in MADRS total score for the MK-1942 daily dose group and Week 1 change from baseline in MADRS total score for the MK-1942 intermittent dose group
- Treatment regimen: MK-1942 or placebo initiated with stable antidepressant therapy without discontinuation of study intervention or stable antidepressant therapy, without initiation of a non-study antidepressant therapy, and without premature unblinding of either the investigator or participant during an envisioned follow-up period of up to 4 weeks (with primary assessment at Week 3 for the MK-1942 daily dose group

PROTOCOL/AMENDMENT NO.: 006-03

[and dose modification allowed for intolerability or non-adherence at or after 2 weeks of treatment] and at Week 1 for the MK-1942 intermittent dose group)

• Population-level summary: mean of the endpoint noted above, compared between treatment regimens (MK-1942 daily dose versus placebo and MK-1942 intermittent dose versus placebo)

(Note: for estimating the HS estimand, data collected after the occurrence of IE1, IE2, IE3 or IE4 will be discarded in the main analysis.)

Supplemental Estimand [based on 'treatment policy strategy' in ICH E9(R1)]

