9.5 Analysis Populations

9.5.1 Efficacy Analysis Populations

The FAS population will serve as the primary population for the analysis of efficacy data in this study. The FAS population consists of all randomized participants who:

- receive at least 1 dose of study intervention
- have at least 1 post-randomization observation for the analysis endpoint subsequent to at least one dose of study intervention
- have baseline data for those analyses that require baseline data

Participants will be included in the treatment group to which they are randomized for the analysis of efficacy data using the FAS population.

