model including calculated change from baseline at Week 1, Week 2, Week 3, and Week 4. The model will handle missing data (both intermittent missing and monotone missing due to dropout) using the missing at random assumption. This model will be used to generate confidence intervals and p-values (compared with placebo). This model assumes a different mean for each treatment at each of the repeated time points in the analysis. In this model, time is treated as a categorical variable so that no restriction is imposed on the trajectory of the means over time. The analysis model will include categorical terms for treatment, number of treatment failures (1; >1) for the current episode of moderate-to-severe MDD, and week, as well as a continuous term for baseline response. In addition, the model will also include the interaction terms of week-by-treatment and week-by-baseline response. The treatment difference in terms of the mean change from baseline at a given time point will be estimated, and as appropriate, tested from the model. An unstructured covariance matrix will be used to model the correlation among repeated measurements. The Kenward-Roger approximation will be used to compute the degrees of freedom [Kenward, M. G. and Roger, J. H. 1997]. A sensitivity analysis will be performed for the primary and key secondary hypotheses to assess the robustness of the primary findings with respect to the handling of missing data. Specifically, a control-based mean imputation approach, with a tipping-point component, will be applied [Mehrotra, D. V., et al 2017]. Details related to this sensitivity analysis will be provided in the sSAP.

As outlined in Table 6, supportive analyses will be performed for the primary and the key secondary hypotheses to assess the robustness of the primary findings with respect to (1) the impact of intercurrent events; and (2) the handling of missing data. Details related to supportive analyses will be provided in the sSAP.

Basic summary statistics will be computed for all efficacy endpoints over time. This minimally includes means and standard deviations for continuous-type endpoints and counts and percentages for categorical endpoints.

Table 6 summarizes the key efficacy analyses.

PROTOCOL/AMENDMENT NO.: 006-03

Table 6 Analysis of Key Efficacy Variables

Endpoint/Variable (Description, Time Point)	Primary vs. Supportive Approach ^a	Statistical Method ^b	Analysis Population	Missing Data Approach	
Primary Hypotheses					

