	Р	Longitudinal ANCOVA ^c with HS estimand	FAS	Model-based ^d	
Change from baseline at Week 3 in MADRS total score (MK-1942 daily dose versus placebo)	S	Longitudinal ANCOVA with HS estimand and Control-Based Mean Imputation ^c	FAS	Control-based mean imputation	
	S	Longitudinal ANCOVA ^c with TPS estimand	FAS	Model-based ^d	
	P	Longitudinal ANCOVA ^c with HS estimand	FAS	Model-based ^d	
Change from baseline at Week 1 in MADRS total score (MK-1942 intermittent dose versus placebo)	S	Longitudinal ANCOVA with HS estimand and Control-Based Mean Imputation ^c	FAS	Control-based mean imputation	
	S	Longitudinal ANCOVA ^c with TPS estimand	FAS	Model-based ^d	
	Seco	ndary Hypotheses			
	Р	Longitudinal ANCOVA ^c with HS estimand	FAS	Model-based ^d	
Change from baseline at Week 3 in HAM-D17 total score (MK-1942 daily dose versus placebo)	S	Longitudinal ANCOVA with HS estimand and Control-Based Mean Imputation ^c	FAS	Control-based mean imputation	
	S	Longitudinal ANCOVA ^c with TPS estimand	FAS	Model-based ^d	
	P	Longitudinal ANCOVA ^c with HS estimand	FAS	Model-based ^d	
Change from baseline at Week 1 in HAM-D17 total score (MK-1942 intermittent dose versus placebo)	S	Longitudinal ANCOVA with HS estimand and Control-Based Mean Imputation ^c	FAS	Control-based mean imputation	
	S	Longitudinal ANCOVA ^c with TPS estimand	FAS	Model-based ^d	

C Confidential

Endpoint/Variable (Description, Time Point)	Primary vs. Supportive Approach ^a	Statistical Method ^b	Analysis Population	Missing Data Approach
	P	Longitudinal ANCOVA ^c with HS estimand	FAS	Model-based ^d
Change from baseline at Week 3 in CGI-S (MK-1942 daily dose versus placebo)	S	Longitudinal ANCOVA with HS estimand and Control-Based Mean Imputation ^c	FAS	Control-based mean imputation
	S	Longitudinal ANCOVA ^c with TPS estimand	FAS	Model-based ^d
	P	Longitudinal ANCOVA ^c with HS estimand	FAS	Model-based ^d
Change from baseline at Week 1 in CGI-S (MK-1942 intermittent dose versus placebo)	S	Longitudinal ANCOVA with HS estimand and Control-Based Mean Imputation ^c	FAS	Control-based mean imputation
	S	Longitudinal ANCOVA ^c with TPS estimand	FAS	Model-based ^d

ANCOVA=Analysis of covariance, CGI-S=Clinical Global Impression-Severity; FAS=full analysis set, HAM-D17=17-item Hamilton Depression Rating Scale; HS=hypothetical strategy; MADRS=Montgomery-Asberg Depression Rating Scale; MDD= major depressive disorder; TPS=treatment policy strategy

- ^a P=Primary approach, S=Supportive approach

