9.9 Sample Size and Power Calculations

9.9.1 Sample Size and Power for Efficacy Analyses

Sample size was determined based on change from baseline in MADRS total score at Week 3 (for MK-1942 daily dose versus placebo) and Week 1 (for MK-1942 intermittent dose versus placebo). This study will randomize 56 participants into the MK-1942 daily dose group, 28 into the MK-1942 intermittent dose group, and 56 into the placebo group. With these sample

Confidential

sizes and assuming an 8% dropout rate after 1 week and 10% dropout rate after 3 weeks, each treatment comparison has at least 80% (marginal) power to demonstrate superiority compared to placebo at the 2-sided 5% α-level; the probability that at least 1 MK-1942 dosing regimen demonstrates superiority compared with placebo is 92%. These calculations assume the underlying SES for change from baseline in MADRS total score at Week 3 (MK-1942 daily dose versus placebo) is -0.6 (eg, corresponds to a mean treatment difference of -6 points and a standard deviation of 10.0 points) and the underlying SES for change from baseline in MADRS total score at Week 1 (MK-1942 intermittent dose versus placebo) is -0.7 (eg, corresponds to a mean treatment difference of -6.5 points and a standard deviation of 9.3 points) and use a normal test. The intermittent dose group has a smaller sample size due to the anticipation that rapid effect will be seen. Therefore, the primary timepoint of interest is Week 1. Because of the shorter time frame, the sample size has been adjusted to account for lower variance, larger treatment difference, and smaller dropout rate versus the daily dose group, where given the 2 week titration, the primary timepoint of interest is Week 3. The underlying treatment SESs are regarded as a clinically relevant for the difference between the 2 treatments. The sample size calculation also accounts for the interim futility analysis. The SESs for this study were based on results of prior publications for MDD and TRD [Sanacora, G., et al 2014] [Canuso, C. M., et al 2018].

Table 10 provides the assumptions for mean differences, standard deviations, and SESs as well as the marginal power for each treatment comparison, and the probability that at least 1 MK-1942 dosing regimen is successful.

Table 10 Primary Assumptions, Marginal Power, and Probabilities for MADRS Total Score

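### The missing-data sensitivity analysis is run on the FAS, which has already removed dosed participants who were never rated after baseline.

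*Combined protocol and SAP*

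**What the plan says.** Section 9.5.1 makes the FAS the efficacy population. Besides a dose and, where needed, a baseline value, a participant must "have at least 1 post-randomization observation for the analysis endpoint subsequent to at least one dose of study intervention". No other efficacy population is defined.

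Section 9.6.1 says that, for the primary and key secondary hypotheses, "a control-based mean imputation approach, with a tipping-point component, will be applied", with the purpose "to assess the robustness of the primary findings with respect to the handling of missing data". Table 6 gives each of the six hypotheses one such row, "Longitudinal ANCOVA with HS estimand and Control-Based Mean Imputation", and lists the FAS in every one. Technical details go to the sSAP, but the population is set in Table 6.

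On timing, Section 1.2 says of Visits 4 to 7 that "MADRS will be administered before the morning dose of study intervention". Section 8.2.1 says the same for all the scales. The Schedule of Activities places the first rating after dosing at Visit 5 (Week 1).

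Under the hypothetical-strategy (HS) estimand, Section 9.3.1 says that "data collected after the occurrence of IE1, IE2, IE3 or IE4 will be discarded in the main analysis". Section 9.9.1 sizes the trial "assuming an 8% dropout rate after 1 week and 10% dropout rate after 3 weeks".

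**The concern.** A control-based or tipping-point analysis asks how far the result depends on what is assumed about unobserved outcomes. Participants with a baseline and a dose but no later rating have the least data, so the assumption matters most for them. Here the analysis set removes them first.

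This matters most for the intermittent regimen. Week 1 is the time point for H2, H4 and H6, and it is also the first scheduled post-dose rating. Loss before Week 1 is therefore the main source of missing data for those hypotheses. If most early leavers fall outside the FAS, the sensitivity result will sit close to the primary result whatever shift is applied, and a reader could take that for robustness.

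There is also an open question of definition. Section 9.5.1 does not say whether a rating that the HS estimand discards, such as an EOT/DC rating after stopping drug, still qualifies a participant for the FAS. If it does not, everyone who stops before Week 1 leaves the HS rows even when rated.

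**Working it through.** **Inputs (Section 9.9.1, Table 10).** 56 daily, 28 intermittent and 56 placebo; dropout 8% at Week 1 and 10% at Week 3. Daily at Week 3: difference 6.0, SD 10.0. Intermittent at Week 1: difference 6.5, SD 9.3. Two-sided 0.05 per comparison. Differences are written as positive benefits.

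**The plan's own figures.** A normal test on the numbers left after dropout, with the futility rule at 60% information, gives power of 83.2% (daily) and 80.3% (intermittent). The plan states 83.0% and 80.8%. The inputs are thus read as the plan intends, and the power is not in dispute.

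**Assumptions.** Dropout is monotone and equal across arms. Let f be the share of pre-Week-1 leavers who enter the FAS. The documents do not give f, so it is run from 1 to 0. The case f = 1 is the same as analysing all dosed participants with a baseline.

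**Formulas.**
- FAS fraction F = 0.92 + 0.08f; excluded = 140 × 0.08 × (1 − f).
- Observed share p = 0.92/F at Week 1 and 0.90/F at Week 3; imputed share q = 1 − p.
- Control-based estimate = p × planned difference.
- Movement of the estimate when imputed active-arm participants are shifted 10 points = 10q.

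| | f = 1 | f = 0.5 | f = 0 |
|---|---|---|---|
| Excluded of 140 | 0 | 5.6 | 11.2 |
| Week 1 imputed share q | 0.080 | 0.042 | 0 |
| Week 1 estimate (intermittent) | 5.98 | 6.23 | 6.50 |
| Week 1 movement per 10-point shift | 0.80 | 0.42 | 0 |
| Week 3 imputed share q | 0.100 | 0.063 | 0.022 |
| Week 3 estimate (daily) | 5.40 | 5.63 | 5.87 |
| Week 3 movement per 10-point shift | 1.00 | 0.63 | 0.22 |

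At f = 0 the 11.2 excluded are 4.5 daily, 2.2 intermittent and 4.5 placebo. The Week 1 row then equals the primary result. At Week 3 the shift has 0.22/1.00, about one fifth, of its full effect.

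**Tipping shift.** Observed-data SEs are 9.3 × √(1/25.76 + 1/51.52) = 2.244 and 10 × √(2/50.4) = 1.992, so the primary z values are 2.90 and 3.01. The tipping shift solves estimate − q × shift = 1.96 × SE. Because the form of the shift and the SE are left to the sSAP, three SEs are used: (1) the observed-data SE; (2) p times that SE; (3) √(p²SE² + (difference + shift)² × pq/n), with n the active-arm FAS size. The table gives the range over the three, in MADRS points (the scale runs 0 to 60).

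| Planned difference | f = 1 | f = 0.5 | f = 0 |
|---|---|---|---|
| Intermittent, Week 1 | 16.5–24.2 | 29–48 | none exists |
| Daily, Week 3 | 15.0–18.9 | 24–31 | 58–94 |

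Under SE (3) with no shift, z is 2.86 / 2.88 / 2.90 at Week 1 and 2.99 / 3.00 / 3.01 at Week 3. Significance at the planned effects does not depend on f.

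**A result just inside 0.05.**
- Intermittent difference 4.6 (z = 4.6/2.244 = 2.05): with all dosed participants it tips at no more than 2.3 points; at f = 0 it cannot tip.
- Daily difference 4.15 (z = 4.15/1.992 = 2.08): with all dosed participants it tips at no more than 2.2 points, against 7 to 11 at f = 0.

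Under SE (1) with all dosed participants, both are already non-significant before any shift.

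**The case against.** The striking figures belong to f = 0, and the protocol works against that. Under Section 7.1, those who stop drug "will still continue to participate in the study". Section 8.11.5 calls for a prompt EOT/DC visit, which includes all three scales. Section 8.1.16 encourages withdrawers to complete it, and Section 8.11.3 allows remote or home visits. At f = 0.8 only 2.2 participants are excluded (140 × 0.08 × 0.2), and the daily estimate is 5.49 against 5.40.

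The plain reading of Section 9.5.1 also favours a higher f. It asks for an observation after a dose, not one that survives the HS discard rule, and the same FAS label serves the treatment-policy rows. On that reading, anyone rated at EOT/DC is in the FAS and can be imputed. Intermittent missing visits, which the monotone assumption ignores, would also leave more to impute.

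Finally, these are supportive rows in a proof-of-concept trial. The tipping ranges depend on SE choices the sSAP has yet to make, and the borderline effects were chosen as illustrations.

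All of this stands as a limit on size. It does not remove the defect. Participants with no post-dose rating, including those who withdraw and decline the EOT/DC visit or are lost to contact, are excluded on any reading. The movement per 10-point shift uses no SE convention. Nor can the sSAP readily repair the population: Table 6 already fixes it, and Section 9 requires a protocol amendment for changes to methods for the primary and key secondary hypotheses.

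**Conclusion.** The concern holds. All six control-based rows use a population that excludes dosed participants never rated after baseline, so the analysis meant to test missing data cannot reach those with the least of it.

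The size is bounded rather than known. With the plan's dropout, monotone and equal across arms, the FAS excludes 0 to 11.2 of 140. The control-based estimate is then 0 to 0.52 points too favourable at Week 1 (6.50 − 5.98) and 0 to 0.47 at Week 3 (5.87 − 5.40). At the upper end the Week 1 rows only repeat the primary result. At the lower end there is no difference. No changed significance conclusion is claimed at the planned effects, and the primary analysis and power are untouched. The practical risk is a borderline result that looks sturdier than it is. The change is worth making because it costs so little.

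**What to change.** - **Section 9.6.1 and Table 6:** run the six control-based/tipping-point rows on all randomized participants with at least one dose and a baseline value. Keep the FAS for the model-based HS and treatment-policy rows. A participant with no post-baseline value adds nothing to the treatment contrast there, so comparison with the primary result still isolates the missing-data assumption.
- **Reporting:** give, by arm, the number of dosed participants with no post-baseline rating. The safety population in Section 9.5.2 already supplies most of this count.
- **Section 9.5.1:** state whether a rating discarded under the HS estimand qualifies a participant for the FAS.
- **Minor and separate, Section 9.3.1:** the treatment-regimen bullet of the treatment-policy estimand repeats the HS condition that none of the four intercurrent events occurs. This contradicts that estimand's own narrative and data rule. Reword it to apply regardless of those events, leaving the dose-modification and assessment-time text as it is. Results are not affected.

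The cost is wording and one analysis-set flag, with no new data. The sensitivity estimates become less favourable by the amounts given in the verdict.

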9.5.2 Safety Analysis Populations

Safety analyses will be conducted in the APaT population, which consists of all randomized participants who received at least 1 dose of study intervention. Participants will be included in the treatment group corresponding to the study intervention they actually received for the analysis of safety data using the APaT population. This will be the treatment group to which

they are randomized except for participants who take incorrect study intervention for the entire treatment period; such participants will be included in the treatment group corresponding to the study intervention actually received.

At least 1 laboratory, vital sign or ECG measurement obtained subsequent to at least 1 dose of study intervention is required for inclusion in the analysis of the respective safety parameter. To assess change from baseline, a baseline measurement is also required.

9.5.3 Pharmacokinetic Analysis Populations

The PP Population consists of the set of data generated by the subset of participants who comply with the protocol sufficiently to ensure that generated data will be likely to exhibit the effects of treatment. Compliance covers such considerations as exposure to treatment, availability of measurements, and absence of important protocol deviations. Important protocol deviations will be identified to the extent possible. Any participants or data values excluded from analysis will be identified, along with their reason for exclusion, in the CSR. At the end of the study, all participants who are compliant with the study procedure as aforementioned and have available data will be included in the PP dataset. This population will be used for the PK analyses.

